### 10.5.2. Study Population

Demographics
Age

 
GSK standard IDSL algorithms will be used for calculating age where birth date will be imputed as follows: 
 
Any participant with a missing day will have this imputed as day '15'.
 
Any participant with a missing date and month will have this imputed as [REDACTED]
 
 
 

Demographics

 
• Birth date will be presented in listings as 'YYYY'.
 
• Completely missing dates of birth will remain as missing, with no imputation applied. Consequently, the age of the participant will not be calculated and will remain missing.
 
• Age, in whole years, will be calculated with respect to the date of screening (Visit 1).
 

Body Mass Index

 
• Calculated as Weight (kg) / [Height (m)]
 

Race

 
• The five high level Food and Drug Administration (FDA) race categories and designated Asian subcategories are: 
 
1. African American/African Heritage
 
2. American Indian or Alaska Native
 
3. Asian 
 
a. Central/South Asian Heritage
 
b. Japanese/East Asian Heritage/South East Asian Heritage
 
c. Mixed Asian Heritage (only required if data exists)
 
 
 
4. Native Hawaiian or other Pacific Islander
 
5. White
 
 
 
• These categories and subcategories will be summarized along with all combinations of high level categories which exist in the data. All five of the high level race categories and the two Asian subcategories must appear on the display even if there are no participants in a particular category, but combinations that do not exist in the data do not need to be represented. Combinations will be represented as the concatenation of the high level category terms, e.g., "White & Asian." The designated Asian subcategories will not be summarized as combinations with other categories.
 
• In addition, the standard race categories collected per IDSL will be summarized along with categories for mixed race. The categories are: 
 
1. African American/African Heritage
 
2. American Indian or Alaska Native
 
3. Asian - Central/South Asian Heritage
 
4. Asian – East Asian Heritage
 
5. Asian – Japanese Heritage
 
6. Asian – South East Asian Heritage
 
7. Asian – Mixed Race
 
8. Native Hawaiian or other Pacific Islander
 
9. White – Arabic/North African Heritage
 
10. White – White/Caucasian/European Heritage
 
11. White – Mixed Race
 
12. Mixed Race
 
 
 
• "Asian – Mixed Race" is only used if more than one Asian category is selected, but no non-Asian races. Similarly, "White – Mixed Race" is only used if both of the White categories are selected, and no non-White races. If multiple races of different types are selected, then the overall "Mixed Race" category is used.
 
• A participant will only be represented in a single category. A participant who selects a combination of races will be counted as "Asian – Mixed Race," "White – Mixed Race," or "Mixed Race," but not in each of the constituent terms. Therefore, the counts will add up to the total number of participants with a response, and the percentages will add to 100%.
 


Treatment Compliance	

 
• Relvar/Breo treatment compliance, calculated as a percentage, will be based on the total number of inhalations taken from the study drug inhaler(s) and the expected number of inhalations to be taken.
 
• The expected number of inhalations will be derived as the expected number of inhalations per day (1 for OD dosing) multiplied by the number of days on study drug based on treatment start date and treatment stop date.
 
• The total number of inhalations taken will be based on the dose counters of the inhalers, which are resupplied during the study. If there is no dose counter information at all then the compliance will be missing, however, as long as the information from one dose counter is present, treatment compliance will be calculated. If a dose counter start count is missing then it will be assumed to be 30. All inhalers dispensed will be used, provided the dose counter stop counts are non-missing.
 
• Treatment compliance will be calculated based on the formula:
 
	
$\text{Compliance} = \left( \frac{\text{Total\_Number\_of\_Inhalations\_Taken}}{\text{Expected\_Inhalations} \times (\text{Stop\_Date} - \text{Start\_Date} + 1)} \right) \times 100$ 
where Total_Number_of_Inhalations_Taken is the total number of doses taken from all inhalers, Expected_Inhalations is equal to 1 and Start_Date and Stop_Date are the earliest treatment start date on or post randomisation and the latest treatment stop date recorded for all the inhalers used in the calculation.
	
Extent of Exposure and Study Duration	

 
• Relvar/Breo on-treatment start date will be defined as the randomisation date and Relvar/Breo Treatment Stop Date will be defined as the latest treatment stop date (from the study treatment compliance eCRF log and treatment discontinuation eCRF page) for the participant. These dates will be used to determine whether a measurement is run-in, on or post-treatment. (See Section 10.3.1 Study Phases). Study conclusion is defined as completion or withdrawal, as applicable.
 
• Duration of exposure to study drug will be calculated as: 
 
◦ Duration of Exposure (days) = Treatment Stop Date – Randomisation Date + 1
 
 
 
• Duration of post-treatment time spent in the study will be calculated as: 
 
◦ Duration of Post-Treatment Study Time (days) = Study Conclusion Date – Treatment Stop Date
 
 
 
• Duration of total time spent in the study will be calculated as: 
 
◦ Duration of Study Time (days) = Study Conclusion Date – Randomisation Date + 1
 
 
 
• Years exposed will be calculated as: 
 
◦ Last treatment stop date - Randomisation Date + 1 / 365.25.
 
◦ Total Years Exposed will be the sum of the year exposed per treatment arm.
 
 
 
	

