## 7.1. Treatments Administered

All subjects will receive Relvar/Breo ELLIPTA, either at the dose they are already prescribed or at the equivalent dose to their current ICS/LABA maintenance therapy if switched onto Relvar/Breo ELLIPTA. Guidance on which Relvar/Breo dose is appropriate, dependent on current therapy is included in Section [7.2](#).

Salbutamol MDI rescue medication will be prescribed to subjects to use as needed throughout the study for relief of asthma symptoms as per usual practice.

Study Treatment Name:	RELVAR/BREO ELLIPTA	Salbutamol MDI
Dosage formulation:	ELLIPTA DPI – 30 doses per device	Metered Dose Inhaler – 200 doses per device
Unit dose strength(s)/Dosage level(s):	100/25 mcg per actuation and 200/25 mcg per actuation	100 mcg salbutamol per actuation
Route of Administration	Inhaled	Inhaled
Dosing instructions:	One inhalation once daily	PRN
Packaging and Labelling	Study Treatment will be provided in a container. Each container will be labelled as required per country requirement.	Treatment will be provided locally and will be labelled as per country requirements.
Manufacturer	GlaxoSmithKline (GSK)	

All subjects will have sensors attached to both their Relvar/Breo ELLIPTA and Salbutamol MDI. It is the type of data provided by the CIS (either Relvar/Breo ELLIPTA alone or Relvar/Breo ELLIPTA and salbutamol MDI), as well as who sees that data (subject alone or subject and HCP) that defines the treatment arms. See [Table 1](#) for a description of what data is fed back to who for each treatment arm. Further information /reference material for the CIS is provided in the SRM.

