### 10.2.2. Definitions of Assessment Windows for Adherence and Rescue Medication Use Analyses

All participants have a sensor on their maintenance and rescue medication to consistently measure their adherence to maintenance and level of rescue medication use in the study. The sensors are attached to participants ELLIPTA Relvar/Breo maintenance treatment and MDI rescue medication from start of Visit 1 until Visit 10. The sensors record the time and date when the Relvar/Breo ELLIPTA cover is opened and closed and the salbutamol MDI rescue medication is actuated.

Study day 1 is defined as the day of randomisation. This could be the day of Visit 2, 3 or 4, dependent on the length of the run-in period. Study day for all other visits, assessments and events are calculated relative to this.

The following information in [Table 5](#) displays which sensor records are summarised for each analysis time period (Analysis Month). Any sensor data recorded post the Month 6 (day 168) time period will not be included in the analysis of ELLIPTA adherence or salbutamol MDI rescue medication use of sensor data.

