1.37.	ITT	IDSL_CM1	Summary of Asthma Concomitant Medications Taken Prior to Screening	Ensure the observations dates are pre-screening visit 1 (there is a specific prior conmeds page in eCRF	SAC [2] DRY RUN [1]
Exposure and Treatment Compliance					
1.38.	ITT	POP_T7	Summary of Exposure to Study Medication	Post-randomisation treatment exposure	SAC [2] DRY RUN [1]
1.39.	ITT	POP_T8	Summary of the Frequency of Puffs Per Day – ELLIPTA Sensor	Programming Note: Repeat for Months 2, 3, 4, 5, 6, Months 4-6, Months 1-6 and Months 1-3. Frequency of puffs per day over the baseline and on-treatment period as defined in the Assessment Windows of RAP	SAC [2] DRY RUN [1]
1.40.	ITT	POP_T8	Summary of the Frequency of Puffs Per Day – MDI Sensor	Programming Note: Repeat for Months 2, 3, 4, 5, 6, Months 4-6, Months 1-6 and Months 1-3. Frequency of puffs per day over the baseline and on-treatment period as defined in the Assessment Windows of RAP	SAC [2] DRY RUN [1]

Study Population Tables					
No.	Population	IDSL / Example Shell	Title	Programming Notes	Deliverable [Priority]
1.41.	ITT	POP_T9	Summary of Treatment Compliance	Post-randomisation compliance Note: Treatment compliance = (Total number of inhalation taken / Expected Inhalation x (Stop date - Start date + 1)) x 100 where Total Number of Inhalations Taken is the total number of doses taken from all inhalers, Expected Inhalations is equal to 1 and Start Date and Stop Date are the earliest treatment start date on or post randomisation and the latest treatment stop date recorded for all the inhalers.	SAC [2] DRY RUN [1]
Others					
1.42.	ITT	POP_T10	Summary of Incidence of Preferred Time of Dosing over the Treatment Period		SAC [2] DRY RUN [1]
1.43.	ITT	POP_T11	Summary of HCP Dashboard Review by Visit	Note: Visits 6/7/8/9 are Healthcare Professional Dashboard reviews for Arm 1 and Arm 3 [1] Action taken – Email/Text/Phone Contact	SAC [2] DRY RUN [1]
1.44.	ITT	POP_T12	Summary of Prior Prescription Details		SAC [2] DRY RUN [1]

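### Dose-counter compliance is understated when an inhaler without a stop count lies between two counted inhalers (SAP 10.5.2)

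*SAP*

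**What the plan says.** Under Treatment Compliance, SAP 10.5.2 defines compliance as 100 times the inhalations taken divided by the inhalations expected.

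- **Numerator.** Doses are read from the inhaler dose counters. "All inhalers dispensed will be used, provided the dose counter stop counts are non-missing". Very little information is enough for a value: "as long as the information from one dose counter is present, treatment compliance will be calculated".
- **Denominator.** One inhalation per day, multiplied by Stop_Date - Start_Date + 1. Start_Date is the earliest start on or after randomisation. Stop_Date is "the latest treatment stop date recorded for all the inhalers used in the calculation".
- **Programming note for Table 1.41 (SAP 10.8.4).** It repeats the formula, but Stop_Date becomes "the latest treatment stop date recorded for all the inhalers", with no limit to the inhalers used in the calculation.

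The Table 1.41 mock shell (SAP 10.9) groups compliance as below 80%, 80 to below 100%, 100 to below 120%, and 120% or more. SAP 6.2.3 presents the result as a summary and a listing. Protocol 5.1 (Dispensing Visits) and 7.8 have the counts recorded when inhalers are exchanged.

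**The concern.** The numerator skips an uncounted inhaler, but the denominator has no matching rule. If counted inhalers lie on both sides of it, the continuous span bridges its days. Missing information is then treated as zero doses, and the error can only lower the result.

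The SAP handles the same problem differently for the sensor. In SAP 10.5.3.1, monthly observed adherence is D1/(D5 - D2 - D3), so device-incident days and days after sensor discontinuation leave the denominator. A reader who sets Table 1.41 beside sensor adherence could see a gap that comes from the formula and not from behaviour. That comparison matters because the dose counter is the planned objective check after randomisation that does not rely on the sensor.

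**Working it through.** The documents give no numerical compliance result, so there is no figure to reproduce. The formula is applied to a participant who takes exactly one dose a day.

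**Inputs**
- Expected use: one inhalation per day (SAP 10.5.2).
- Device size: "ELLIPTA DPI – 30 doses per device" (Protocol 7.1).
- Length: 168 days. Month 6 ends at day 168 in SAP 10.2.2, and Visit 10 is scheduled for day 168.
- Assumption: consecutive inhalers without gaps, changed every 30 days (five of 30 days and one of 18) or every 28 days (six of 28 days). Both give six inhalers.

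**Formula:** compliance = 100 x doses from counted inhalers / (Stop_Date - Start_Date + 1).

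**Check:** with every stop count present, both wordings give 168/168 = 100%.

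**Results for a fully adherent participant (30-day changes unless stated)**

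| Stop counts missing | SAP 10.5.2 (inhalers used) | Table 1.41 note (all inhalers) |
|---|---|---|
| First inhaler | 138/138 = 100% | 138/168 = 82.1% |
| Last inhaler | 150/150 = 100% | 150/168 = 89.3% |
| Last two | 120/120 = 100% | 120/168 = 71.4% |
| All but the first | 30/30 = 100% | 30/168 = 17.9% |
| One in between | 138/168 = 82.1% | 82.1% |
| One in between, 28-day changes | 140/168 = 83.3% | 83.3% |
| Two in between | 108/168 = 64.3% | 64.3% |
| Two in between, 28-day changes | 112/168 = 66.7% | 66.7% |
| All but first and last | 48/168 = 28.6% | 28.6% |

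For a participant who stops early after three inhalers, with the middle one uncounted, the result is 56/84 or 60/90, both 66.7%.

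Under SAP 10.5.2 the distortion therefore arises only for an inhaler between two counted ones. Under the literal Table 1.41 note it arises wherever the uncounted inhaler lies, so the same participant can receive different values from the two instructions.

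**The case against.** The strongest counter-argument is procedural. Protocol 5.1 requires participants to bring the used ELLIPTA in order to collect the next one, and remaining doses are part of the minimum data captured at that visit. An inhaler in the middle of the sequence is therefore the least likely to lack a count. The likeliest is the last one, for instance after loss to follow-up, and SAP 10.5.2 handles that case correctly. This bears on how often the problem occurs and it stands. It does not make the rule right when the problem does occur, and the SAP itself provides for missing stop counts.

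Several stronger readings are tempting but not supported:

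- A reader might infer that any uncounted inhaler lowers the result. SAP 10.5.2 restricts the dates to the inhalers used, so an uncounted first or last inhaler drops out of both parts of the ratio. Only the Table 1.41 note would support the wider reading.
- A reader might infer that one missing count labels a perfect user non-compliant. Over 168 days, 82-83% stays in the 80 to below 100% band, and the SAP sets no compliance threshold, only display bands.
- A reader might infer a bias between arms. The documents give no rate of missing counts, overall or by arm, so this is possible but not shown.
- A reader might take Table 1.41 as the only measure of maintenance use that is independent of the sensor. MARS-A (Protocol 9.1.3.5; SAP Table 2.31) is another, although it is self-reported.

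It is also fair to say that the table feeds no test, model or imputation.

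**Conclusion.** The point holds in a narrow form, and its severity is minor. As SAP 10.5.2 is written, an inhaler without a stop count lying between two counted inhalers understates compliance. For full adherence over 168 days with six inhalers, the value falls from 100% to about 82-83% with one such inhaler and to 64-67% with two. The below-80% band is reached with two, or with one when exposure is short (66.7% with three inhalers). Separately, SAP 10.5.2 and the Table 1.41 note disagree on which inhalers set the dates.

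The figures rest on perfect daily use, consecutive inhalers without gaps, and changes every 28 or 30 days. The effect on the reported table cannot be sized, because the documents do not say how often stop counts will be missing. The primary endpoint is measured by the sensor and is unaffected.

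**What to change.** 1. In SAP 10.5.2, keep the continuous span from Start_Date to Stop_Date of the inhalers used, but subtract the days assigned to any inhaler in that span with no stop count. Assign to it the days from its dispensing date to the day before the next inhaler is dispensed, and count each calendar day once. The examples above then become 138/(168 - 30) = 100% and 108/(168 - 60) = 100%.
2. Align the Table 1.41 programming note with SAP 10.5.2, so that both limit the dates to the inhalers used.
3. Show the number of excluded inhalers by arm in Table 1.41.

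Summing start-to-stop days plus one over the counted inhalers looks simpler but brings two new errors. If one inhaler is returned and the next dispensed on the same day, six inhalers have five changeover days counted twice, and a perfect user with nothing missing scores 168/(168 + 5) = 97.1%. It also removes real gaps: a participant 14 days late for a refill has taken 154/168 = 91.7% but would show 154/154 = 100%. Subtracting from the span keeps a late-refill gap between counted inhalers in the denominator. A gap directly after an uncounted inhaler does go out with it, because the two cannot be told apart.

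The cost is a small programming change and two edits to the SAP, using dispensing dates that are already collected. For the participants affected, compliance will rest on fewer days.

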### **Flexible Run-in**

Following inclusion at screening all subjects will receive Relvar/Breo ELLIPTA DPI maintenance therapy and salbutamol MDI rescue medication and be instructed to take these as prescribed.

Instruction on correct use of the Relvar/Breo ELLIPTA DPI and salbutamol MDI will be provided, particularly in the case of subjects previously using other devices, and/or using medication requiring twice-daily dosing.

Both the Relvar/Breo ELLIPTA and salbutamol MDI medication used by all subjects included on the study will have a sensor fitted and switched on at the clinic visit. However, during this run-in period, there will be no information provided to the subjects or HCPs on their adherence to Relvar/Breo ELLIPTA or on their use of salbutamol MDI. Subjects will also be instructed in fitting the sensors onto both the ELLIPTA and MDI.

The run-in period can last for 1, 2 or 3 months, dependent on a subject's ACT at end of each month of the run-in period.

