#### **6.2.3. Study Medication Exposure and Compliance**

Duration (days) of exposure to study medication will be calculated based on randomisation date and latest (stop) of all dates recorded for the participant. Duration will be summarised categorically and with descriptive statistics. Total years exposed to Relvar/Breo after randomisation will also be presented. Further details are presented in Section 10.5 Appendix 5: Derived and Transformed Data

Calculation of Relvar/Breo study medication compliance after randomisation, will be based on the ELLIPTA device dose counter (which displays the number of doses remaining) as described in Section 10.5 Appendix 5: Derived and Transformed Data. Treatment compliance (calculated as a percentage) will be summarised categorically and with descriptive statistics.

All exposure and compliance data will be listed.

A summary of the number of puffs per day as recorded by the ELLIPTA Relvar/Breo and MDI sensors will be summarised and graphically presented.

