## 10.3. Appendix 3: Study Phases and Treatment Emergent Adverse Events

### 10.3.1. Study Phases

Since participants are on Relvar/Breo study treatment from the time they enter run-in, assessments and events will be classified according to time of occurrence relative to the randomisation date and last stop date of Relvar/Breo treatment. The randomisation and latest exposure treatment stop dates will be used to determine whether an assessment or event was during pre-screening treatment, run-in treatment, on-treatment or post-treatment. If it is not possible to tell whether an assessment or event was on-treatment or not, it will be considered as on-treatment.

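### Dose-counter compliance is described as post-randomisation, but its numerator is not limited to post-randomisation inhalers; programmed literally, run-in doses inflate it 1.17- to 1.50-fold

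*SAP*

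**What the plan says.** SAP 6.2.3 sets the scope: "Calculation of Relvar/Breo study medication compliance after randomisation, will be based on the ELLIPTA device dose counter". The programming note for Table 1.41 (SAP 10.8.4) opens with "Post-randomisation compliance".

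The derivation is in SAP 10.5.2, under Treatment Compliance. Compliance is 100 times the inhalations taken, divided by one inhalation per day over the days from Start_Date to Stop_Date inclusive.

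- **Numerator.** "All inhalers dispensed will be used, provided the dose counter stop counts are non-missing". The formula's key then says that the count "is the total number of doses taken from all inhalers". The only stated condition is a recorded stop count.
- **Denominator.** The two dates that bound the period are defined thus: "the earliest treatment start date on or post randomisation and the latest treatment stop date recorded for all the inhalers used in the calculation". The Table 1.41 note repeats the all-inhalers wording and the dates, but without the closing words that tie the dates to the inhalers used in the calculation.

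Study inhalers are in use before randomisation. Protocol 5.1 (Flexible Run-in) says "Following inclusion at screening all subjects will receive Relvar/Breo ELLIPTA DPI maintenance therapy", and SAP 10.3.1 notes "Since participants are on Relvar/Breo study treatment from the time they enter run-in". Under Protocol 5.1 (Dispensing Visits) and 7.8, counter readings are recorded at dispensing visits and go to the eCRF, so run-in counts will be in the database.

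**The concern.** The two halves of the ratio can cover different periods. The denominator is explicitly limited to time from randomisation; the numerator is not. If run-in inhalers enter the numerator, the result depends on how long the participant spent in run-in as well as on how much of the drug was used.

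Dose-counter compliance is the only device-based count of post-randomisation ELLIPTA use besides the sensor. No planned analysis compares the two, but in a trial about adherence a reader will naturally set Table 1.41 beside the sensor results. An inflated table would show poor users as compliant and some perfect users as over-users.

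**Working it through.** The documents give no compliance value to reproduce; the listing shell in SAP Appendix 9 holds only placeholder values. The check is therefore direct arithmetic on the SAP formula.

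**Inputs**
- Run-in R of 1, 2 or 3 months (Protocol 5.1), taken as 28, 56 or 84 days. A 28-day month matches the analysis windows in SAP 10.2.2.
- Treatment period T = 168 days (Schedule of Activities, V10; SAP 10.2.2).
- One expected dose per day (SAP 10.5.2).
- Bands in the Table 1.41 shell: under 80%, 80% to under 100%, 100% to under 120%, and 120% or more.
- a = true proportion of doses taken, assumed constant over run-in and treatment.

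**Formulas**
- Literal reading, with run-in inhalers counted: 100 × a × (R + T) / T.
- Restricted reading, with both halves post-randomisation: 100 × a × T / T = 100 × a.

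**Results, literal reading, T = 168**

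| | R = 28 | R = 56 | R = 84 |
|---|---|---|---|
| Factor (R + 168)/168 | 196/168 = 1.167 | 224/168 = 1.333 | 252/168 = 1.500 |
| a = 1.0 | 116.7% | 133.3% | 150.0% |
| a = 0.7 | 81.7% | 93.3% | 105.0% |
| True adherence above which the score passes 100%: 100 × 168/(R + 168) | 85.7% | 75.0% | 66.7% |
| True adherence at which the score reaches 80%: 80 × 168/(R + 168) | 68.6% | 60.0% | 53.3% |

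On the restricted reading the scores are 100% and 70% at every run-in length.

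**Sensitivity.** The V10 window is ±7 days. Varying T from 161 to 175 gives a perfect user 116.0–117.4%, 132.0–134.8% and 148.0–152.2%, and a 70% user with an 84-day run-in 103.6–106.5%. These figures start the denominator at randomisation. If the first inhaler started after randomisation begins later, the denominator is shorter and the literal score is higher still.

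**Inhaler in use across randomisation.** Devices hold 30 doses (Protocol 7.1). If each is used up before the next is started, a 70% user stands as follows at randomisation:
- R = 28: 0.7 × 28 = 19.6 doses taken; 30 − 19.6 = 10.4 left; 10.4 / 0.7 ≈ 15 days of use.
- R = 56: 39.2 taken; 60 − 39.2 = 20.8 left; 20.8 / 0.7 ≈ 30 days.
- R = 84: 58.8 taken; 60 − 58.8 = 1.2 left; 1.2 / 0.7 ≈ 2 days.

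**The case against.** The best defence is that the scope is already set. SAP 6.2.3 and the Table 1.41 note both say post-randomisation. The all-inhalers sentence closes a bullet on missing counter data, so it may be a missing-data rule and not a rule about study phase. The dates refer to the inhalers used in the calculation, which fits a set made up only of inhalers started on or after randomisation. On that reading an inhaler started in run-in drops out, and nothing is inflated.

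This stands to the extent that a reader should not infer that the SAP has decided to count run-in inhalers. No section expressly includes or excludes them. It does not remove the problem: the derivation states a numerator rule with one condition, that condition is not study phase, and the Table 1.41 note repeats the rule without the words on which the restricted reading leans. Two programmers could follow the text in good faith and produce different tables.

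Other limits also stand:
- A reader might infer that a 70% user generally scores above 100%. That happens only after an 84-day run-in, which requires ACT of 20 or more at V2 and V3 and below 20 at V4. The documents give no distribution of run-in length.
- It would be wrong to call this the only check on sensor adherence. MARS-A, a self-reported adherence scale, is also collected and summarised.
- Scores of 133% or 150% in perfect users would be conspicuous, and Table 1.41 is part of the dry run, so literal programming might be caught. That is a reason to settle the wording before programming.
- Protocol 6.4 speaks of study treatment being dispensed at V2, which suggests a fresh inhaler at randomisation. It does not prove one, because Protocol 7 defines study treatment to include devices.

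**Conclusion.** The point holds as a conflict between the stated scope of the measure and the rule for its numerator. If the rule is programmed as written, compliance is inflated by 1.17, 1.33 or 1.50 for run-ins of 28, 56 or 84 days. A 70% user then leaves the under-80% band at every run-in length. A perfect user lands in the band for 120% or more after the two longer run-ins. This assumes 28-day months, 168 treatment days, constant use and complete stop counts.

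The consequence is limited to a descriptive table (Table 1.41) and its listing (Listing 28). A reader might infer a threat to the efficacy result; the documents do not support that. Protocol 7.8 makes the sensor the primary compliance measure, the primary endpoint has its own sensor windows, and dose-counter compliance defines no population, covariate or intercurrent event. Run-in length is settled before randomisation, so no arm is expected to be favoured.

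**What to change.** In SAP 10.5.2, replace the opening of "All inhalers dispensed will be used, provided the dose counter stop counts are non-missing" so that the rule covers *all inhalers with a treatment start date on or after randomisation*, keeping the stop-count condition. Make the same restriction where the formula's key and the Table 1.41 note refer to all inhalers. Keep Start_Date as the earliest start date among those inhalers.

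Add one rule for an inhaler in use across randomisation: where a counter reading at the randomisation visit exists, count only the doses after that reading and start the denominator at randomisation.

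The cost is SAP wording and one derivation, with no new data. The downside is coverage. Without such a reading, or a new inhaler at randomisation, the days left on the run-in inhaler are lost: for a 70% user about 15 days after a 28-day run-in and about 30 after a 56-day run-in. That loss is greater for this user than for a perfect user, who has only 2 or 4 doses left at those points (30 − 28; 60 − 56), so the table footnote should state it.
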